Rationale: Immune checkpoint inhibitors (ICIs) are widely used as treatment for multiple cancer types and the number of patients with long-term disease control after ICIs is increasing. However, the use of ICIs is associated with adverse events (AEs) which can have a negative impact on quality of life (QoL). These AEs include oral manifestations, like alterations in taste and smell, xerostomia, and oral mucosal disorders, and could lead to unwanted weight loss. However, the characteristics of taste and smell dysfunction and xerostomia after treatment with ICIs are unknown. More insight in this phenomenon should be gained to make health care professionals aware of this problem to help patients cope with these AEs.

Objective: To determine the prevalence of taste and smell dysfunction in patients more than two years after start of ICI therapy - compared with a control group of caregivers. Secondary objective: to assess the association between taste and smell dysfunction, and saliva secretion rate, saliva composition (pH, electrolyte and protein composition) and subjective feeling of a dry mouth (xerostomia) in patients more than two years after start of ICI therapy - compared with a control group of caregivers.

Study design: Observational cross-sectional study.

Study population: Patients (aged ≥18 years) with melanoma, non-small cell lung cancer (NSCLC) or urogenital cancers who have started treatment with an ICI (CTLA-4 inhibitor, PD-(L)1 inhibitor, or both) ≥2 years ago, and their caregivers.

Main study parameters/endpoints: Taste and smell dysfunction, measured using taste strips and Sniffin' Sticks. Secondary parameters are salivary flow rate, salivary pH. proteins and electrolytes, xerostomia and perceived taste and smell dysfunction.

Nature and extent of the burden and risks associated with participation, benefit and group relatedness: Participation in the study will include one study visit of approximately 1,5 hour. If possible, the study visit will be combined with a regular follow-up visit. In this study, no invasive procedures will be performed. The results of the full study group will be used to guide future interventions and support for cancer patients treated with ICIs.

1. INTRODUCTION AND RATIONALE

Immune checkpoint inhibitors (ICIs) are widely used as treatment for multiple cancer types, including renal cell carcinoma (RCC), melanoma and non-small cell lung cancer (NSCLC)(1). It is estimated that 44% of the patients with cancer may derive benefit from ICIs and 13% would have a response to the ICIs(2). ICIs block the immune inhibitory signals of the tumour, so T cells can target cancer cells and exert an anti-tumour effect(3). Effective specific targets of ICIs are the immune-regulatory checkpoints cytotoxic T-lymphocyte antigen-4 (CTLA-4), Programmed death 1 (PD-1) and PD ligand 1 (PD-L1)(4).

The use of ICIs is associated with adverse events (AEs), mostly due to immune system activation. The AEs have various characteristics: they can be mild or life-threatening, can have a short or long onset and can develop in different organ systems(5). The most common affected systems are the gastrointestinal tract, skin, endocrine glands, and liver(6).

Oral manifestations have also been described(7,8). Xerostomia (the feeling of a dry mouth) was reported in 69% of patients with cancer using ICIs, oral mucosal disorders in 33%, and dysgeusia (altered taste) in 24%(9). However, these previous studies did not report whether these patients were surveyed for these oral side effects or the numbers were based on problems spontaneously reported by patients. Oral side effects are often neglected by both patients and health care professionals, and therefore are easily underreported if not structurally surveyed among patients(10).

Due to long-term survival, patients have to cope with continuing side-effects for a longer period of time(11). Chronic AEs have been found in more than 40% of the patients, mostly endocrinopathies and rheumatological toxicities(12).

Also changes in taste and smell have been found in long-term responders using ICIs. A patient with remaining taste changes three years after immunotherapy discontinuation has been described by our group(13). Furthermore, a study which investigated the initiation of oral AEs in patients using ICIs found that these AEs mostly develop in the first 100 days, but can also develop after two years(9). However, these oral AEs were mentioned spontaneously and an objective determination of taste and smell dysfunction and their prevalence after treatment with ICIs is still lacking.

As mentioned previously, a phenomenon that has been found in patients treated with ICIs is xerostomia. Possibly due to T cell-meditated inflammation, the salivary gland is affected(14). It has been hypothesized that oral dryness could be a chronic AE of ICI treatment: the salivary gland can be irreversibly damaged, which would lead to diminished saliva production and secretion(12). The reduced saliva secretion (hyposalivation) is often associated with the subjective feeling of a dry mouth (xerostomia). Oral dryness can contribute to taste disturbances, as saliva dissolves foods and makes it possible that taste molecules bind to gustatory receptor cells. Furthermore, hyposalivation is a risk factor for oral diseases, including dental caries.

Saliva consists of multiple electrolytes and proteins. The electrolytes include sodium, potassium, chloride, magnesium, calcium, bicarbonate and phosphate(15). The proteins in saliva have many biological activities, including antibacterial and antifungal activity, food digestion and promoting wound healing. Therefore alterations in salivary electrolytes and proteins can lead to oral diseases and taste problems, as they make the dissolving of food and

thereby taste possible(16). The ion concentration and pH of the saliva will mostly be altered if the salivary flow rate is low(16). It could therefore be possible that the electrolyte composition of saliva is altered in patients with cancer treated with ICIs suffering from hyposalivation. However, electrolyte and protein analysis of saliva has not been performed in patients treated with ICIs.

Alterations in taste and smell, xerostomia, and oral mucosal disorders can have impact on quality of life (QoL) and could lead to unwanted weight loss(17,18). Moreover, distribution of household roles and social functioning have also been found to be associated with taste and smell dysfunction(19,20). More insight in the prevalence and impact of taste and smell alterations, and xerostomia should be gained to make health care professionals aware of this problem and to help patients cope with these AEs.

A cohort with melanoma, NSCLC and urogenital cancer patients treated with ICIs and their caregivers has already been built up. In this cohort, we will determine the prevalence and characteristics of taste and smell dysfunction of patients surviving more than two years after starting immune checkpoint inhibitor therapy. Furthermore, the association of taste and smell dysfunction to pH, saliva secretion rate, saliva composition and xerostomia will be assessed.

2. OBJECTIVES

Primary Objective:

• To determine the prevalence of taste and smell dysfunction in patients more than two years after start of ICI therapy - compared with a control group of caregivers.

Secondary Objective(s):

- To assess the association between taste and smell dysfunction, and saliva secretion rate, saliva composition (pH, electrolyte and protein composition) and subjective feeling of a dry mouth (xerostomia) in patients more than two years after start of ICI therapy compared with a control group of caregivers.
- To assess the impact of taste and smell dysfunction in patients more than two years after start of ICI therapy.

3. STUDY DESIGN

In this cross-sectional study, patients with melanoma, NSCLC or urogenital cancer ≥ 2 years following ICI therapy and their caregivers will be included. We will include patients who have previously participated in the study "Quality of life, cognitive function, and physical fitness of patients surviving more than 2 years after immune checkpoint inhibitor therapy" (METc 2018/158, clinicaltrials.gov NCT03946007) and additional patients who are under control at the departments of Medical Oncology and Pulmonary Disease and did not participate in this previous studyA patient cohort of 70-120 patients and 70-120 of their caregivers has already been built and patients who have given permission to be approached for future research again will be invited for our study.

Patients can be approached in two ways: 1) Patients will be asked during an outpatient clinic appointment by their clinical doctor if they can be approached afterwards by the investigator. When permission is given, the investigator will explain the study design and give the patient and the caregiver both a letter. These letters explains the study design and includes an informed consent form, 2) Patients who do not have an outpatient clinic appointment in the near future will be sent the letter with the study design and the informed consent form. In this letter, we will also ask each participant to invite their caregiver to participate in this study. For this, a separate letter directed at the caregiver will be sent to the participant. Patients and caregivers are asked to contact the investigator team if they are willing to participate. If the patient consents, a single appointment will be made during a regular follow-up visit to the outpatient clinic. If the caregiver consents too, we will make an appointment with both participants at the same time, if possible. Patients can participate alone if the caregiver is not willing to participate, and vice versa.

During this visit, if patients and caregivers have no questions regarding the study or the study information that was sent, they are first asked to sign the informed consent. Next, saliva will be collected, and taste, smell and dry mouth will be subjectively and objectively be measured. Afterwards, characteristics will be taken from the patients' electronic file, including age, gender, medical history and medication use. As the caregivers do not have a medical file, they are asked for these characteristics.

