4. STUDY POPULATION

4.1 Population (base)

The participants in this study will be derived from an existing cohort of 70-120 patients who have undergone ICI treatment and have not received other systemic treatment (METc 2018/158, clinicaltrials.gov NCT03946007). These patients have been previously included in a cross-sectional study in which health-related quality of life, neurocognitive function, endocrine function, cardiovascular risk, physical fitness, mood disorders, sexual problems, and work participation were investigated. Patients have survived two years or more after the first cycle of an immune checkpoint inhibitor for melanoma, NSCLC, or urogenital cancer. Furthermore, the quality of life of the caregivers of these patients was studied.

The participants of this previously performed study who have given permission to be approached again, will be asked to participate in this study. In addition, to complete the required number of participants, additional patients from the departments of Medical Oncology and Pulmonary Disease, who were not included in the previously mentioned cohort, but who meet the criteria for this study, will be invited to participate in the study. Furthermore, a part of the caregivers of these patients have also been included in this previously mentioned cohort and has given permission to be approached again. The caregivers will act as control group for practical purposes, as they often accompany the patient on the hospital appointments. Furthermore, caregivers tend to have the same basic characteristics as the patients, and therefore, these characteristics will be distributed more equally in both groups. If a patient has a new caregiver, this new caregiver can also be asked to participate in this study instead of the previously included caregiver. Patients can also participate if they don't have a caregiver. The caregivers of the additional patients will also be invited.

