8.2 Study procedures

Both patients and caregivers are asked not to smoke, brush teeth, eat, or drink anything except water one hour before the tests. Then, unstimulated and chewing-stimulated saliva will be collected, the salivary flow rate will be measured using standardized procedures, and patients and caregivers will fill in two questionnaires regarding perceived taste and smell dysfunction. Taste and smell dysfunction will be assessed with taste strips and Sniffin' Sticks. To assess subjective taste and smell perception, and the impact of taste and smell dysfunction, the Chemotherapy-induced Taste Alteration Scale (CiTAS) questionnaire, the Patient-Generated Subjective Global Assessment (PG-SGA) questionnaire, the Appetite, Hunger and Sensory Perception (AHSP) and the Questionnaire of Olfactory Disorders (QOD) will be used. Subjective xerostomia will be assessed with the Dutch versions of the Xerostomia Inventory (XI) and the Regional Oral Dryness Inventory (RODI). The results of the patients will be compared with the caregivers. Salivary flow rate and pH will be measured immediately after collection, and subsequently the saliva will be stored at -80°C until biochemical analysis. Below, the tests and examinations are explained in more detail.

Taste dysfunction

Taste dysfunction will be objectively measured with "Taste Strips" (Burghart, Wedel, Germany)(23). Strips with an impregnated taste solution will be placed on the participants' tongue. The taste solutions contain the basic tastes bitter, sweet, sour and salty in four different concentrations, thus 16 tests will be performed. The strips will be randomly administered and participants are asked which taste they notice. A right answer gives one point and a total of 16 point can be obtained.

Smell dysfunction

Smell dysfunction will be objectively measured with "Sniffin' Sticks" (Burghart, Wedel, Germany)(24). Pens filled with liquid odorants are presented to the participants' nose. Participants will smell 16 different scents with an interval of minimal 30 seconds to

prevent desensitization. For each scent, participants will choose between four options from a multiple choice card. Smell threshold will be measured with "Sniffin' Sticks" with different odor concentrations.

Saliva (flow rate, pH and elektrolytes)

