10. STATISTICAL ANALYSIS

This study aims to investigate the prevalence of taste and smell dysfunction in a predefined cohort of melanoma, NSCLC and urogenital cancer patients. Results will be reported as mean (standard deviation) and median (range) for parametric and non-parametric continuous variables, respectively. Categorical data will be presented as N and percentages.

Participants and their caregivers will be compared using Mann Whitney U test or independent T-test, depending on data distribution. For ordinal data, Chi-square tests will be performed. Correlations between perceived and objective taste and smell dysfunction will be studied with Pearson's rho or Spearman's rho, depending on data distribution.

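### Smoking is not named among the characteristics to record and no adjusted comparison is planned, so a patient-caregiver imbalance in smoking could be neither shown nor adjusted for, mainly because caregivers have no file

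*Combined protocol and SAP*

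**What the plan says.** Section 3 covers the background data in two sentences. For patients, the characteristics come from the electronic file, "including age, gender, medical history and medication use". For controls, "As the caregivers do not have a medical file, they are asked for these characteristics". Smoking is not named there, nor in the eligibility criteria (4.2, 4.3), the endpoints (8.1) or the statistics (10 to 10.2). Its one appearance is in Section 8.2, where patients and caregivers are "asked not to smoke, brush teeth, eat, or drink anything except water one hour before the tests".

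The population in Section 3 is mixed: "patients with melanoma, NSCLC or urogenital cancer ≥ 2 years following ICI therapy and their caregivers will be included". The case for caregivers as controls is made in Section 4.1, partly on practical grounds and partly because "caregivers tend to have the same basic characteristics as the patients". No matching is specified, and Section 3 lets a patient or a caregiver take part without the other.

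The group comparison in Section 10 is: "Participants and their caregivers will be compared using Mann Whitney U test or independent T-test, depending on data distribution". Chi-square tests are added for ordinal data, and Section 10.2 adds correlations. No covariate and no regression model appear.

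**The concern.** The comparison is not randomised. Any effect attributed to checkpoint inhibitors rests on patients and caregivers being alike in whatever else influences taste, smell and saliva. The protocol treats recent smoking as something to standardise at the visit, but one hour of abstention says nothing about habitual or past smoking. Similarity in smoking is a natural thing to question when one of the three patient groups has lung cancer, although the documents give no smoking figures for any group.

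The two groups are also not equally well covered. A patient's smoking may be in the file, while a caregiver's is known only if someone asks. A covariate known in one group only cannot be used in an adjusted comparison, nor can it show that the groups are balanced. If patients smoke or smoked more than caregivers, and smoking impairs the measures, part of the difference would be read as an effect of treatment.

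**Working it through.** **1. The plan's own figure.** Section 4.4 expects dysfunction in 25% of patients and 5% of caregivers and gives 49 per group at 95% confidence and 80% power. With the two-sided pooled formula and no continuity correction:

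n = [1.96·√(2·0.15·0.85) + 0.842·√(0.25·0.75 + 0.05·0.95)]² / 0.20² = (0.990 + 0.408)² / 0.04 ≈ 48.8, rounded up to 49.

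Power at 49 per group is 80.1%, so the figure reproduces. The planned prevalence ratio is 0.25/0.05 = 5.

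**2. Spurious ratio from smoking alone.** Let a share p1 of patients and p0 of caregivers be smokers, and let smoking multiply the risk of dysfunction by RR. With no effect of treatment, the apparent ratio is

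B = [1 + p1(RR − 1)] / [1 + p0(RR − 1)].

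The smoking shares and RR below are assumptions; the documents supply none of them. The patient column is 5% × B. The last column is 25%/B, the patient rate net of smoking if 25% were observed and the two effects multiply.

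| p1 vs p0 | RR | B | Patients, no treatment effect | Net of smoking if 25% observed |
|---|---|---|---|---|
| equal | any | 1.00 | 5.0% | 25.0% |
| 40% vs 20% | 2 | 1.4/1.2 = 1.17 | 5.8% | 21.4% |
| 60% vs 20% | 2 | 1.6/1.2 = 1.33 | 6.7% | 18.8% |
| 80% vs 30% | 2 | 1.8/1.3 = 1.38 | 6.9% | 18.1% |
| 80% vs 30% | 3 | 2.6/1.6 = 1.63 | 8.1% | 15.4% |

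The 80% versus 30% rows are an extreme contrast. The comparison pools melanoma, lung and urogenital cancer, and the documents do not give the mix.

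**3. Set against the plan.** Smoking alone moves patients from 5% to between 5.8% and 8.1%, far short of 25%. With 49 per group, the chance of a two-sided significant result would be about 5.4% to 9.5% (normal approximation), against a nominal 5%. On the other side, an observed difference of 25 − 5 = 20 points would correspond to 21.4 − 5 = 16.4 down to 15.4 − 5 = 10.4 points net of smoking.

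**4. What adjustment can carry.** The planned rates imply 0.25·49 + 0.05·49 = 14.7, about 15 cases of dysfunction in 98 participants. Group, age, sex, three-level smoking (two terms) and pack-years (one term) make six terms, or 14.7/6 ≈ 2.5 cases each. With a single binary smoking term there are four, or 14.7/4 ≈ 3.7 each. A model of the scores uses all participants and does not depend on the number of cases.

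**The case against.** Several points on the other side stand. The list in Section 3 is introduced as examples, so the documents show that smoking is not named, not that it will not be collected. The case report form is not among them. A reader might also infer that smoking could never be adjusted for later, and the documents do not support that. Patient files can be consulted again. The earlier cohort study covered cardiovascular risk, and Section 11.2 says the cohort's patients and caregivers agreed to be approached again.

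These routes are partial. Section 4.1 links cardiovascular risk to the patients and mentions only quality of life for caregivers. It does not say that smoking was recorded or that the data will be linked. Newly recruited patients, their caregivers and replacement caregivers may lie outside that cohort.

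It is also fair that the one-hour request is a standardisation step for acute interference. It is not evidence that past smoking alters these tests, and nothing in the documents supports a two- or threefold effect. Finally, recording smoking changes nothing unless an adjusted analysis uses it, and Section 10 plans none for any covariate.

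**Conclusion.** The point holds as a gap in data collection and analysis that is cheap to close. Followed as written, the protocol may leave smoking unrecorded for the control group, and its unadjusted tests would make no use of smoking even if it were recorded. The firm part is the caregiver side; for patients the information may well exist.

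The size is unknown. The range of about 1.2 to 1.6 for the spurious prevalence ratio depends wholly on assumed smoking shares and an assumed two- to threefold effect, and it falls to 1 if smoking is balanced. A reader might infer that smoking could explain the whole expected result. The arithmetic does not support that, since the planned ratio is 5. What remains is possible inflation of the estimated difference. Without smoking data from both groups, a reader of the results could not tell whether it had occurred.

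**What to change.** - **Section 3:** name current and past smoking among the characteristics, and ask it in the same words of patients and caregivers rather than taking it from the file for one group.
- **Results:** report smoking by group, so that balance or imbalance is visible.
- **Section 10:** add a sensitivity analysis that compares taste strip and Sniffin' Sticks scores between patients and caregivers by linear regression, adjusted for age, sex and a single binary smoking term. Define that term in advance.
- **Prevalence:** keep any adjusted model of dysfunction minimal, given about 15 expected cases. Three-level smoking plus pack-years would take three terms and is more than those cases can carry.

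The cost is about two questions per participant, one smoking term in the model and slightly wider intervals. The planned unadjusted tests can stay as they are.

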4. STUDY POPULATION

4.1 Population (base)

The participants in this study will be derived from an existing cohort of 70-120 patients who have undergone ICI treatment and have not received other systemic treatment (METc 2018/158, clinicaltrials.gov NCT03946007). These patients have been previously included in a cross-sectional study in which health-related quality of life, neurocognitive function, endocrine function, cardiovascular risk, physical fitness, mood disorders, sexual problems, and work participation were investigated. Patients have survived two years or more after the first cycle of an immune checkpoint inhibitor for melanoma, NSCLC, or urogenital cancer. Furthermore, the quality of life of the caregivers of these patients was studied.

The participants of this previously performed study who have given permission to be approached again, will be asked to participate in this study. In addition, to complete the required number of participants, additional patients from the departments of Medical Oncology and Pulmonary Disease, who were not included in the previously mentioned cohort, but who meet the criteria for this study, will be invited to participate in the study. Furthermore, a part of the caregivers of these patients have also been included in this previously mentioned cohort and has given permission to be approached again. The caregivers will act as control group for practical purposes, as they often accompany the patient on the hospital appointments. Furthermore, caregivers tend to have the same basic characteristics as the patients, and therefore, these characteristics will be distributed more equally in both groups. If a patient has a new caregiver, this new caregiver can also be asked to participate in this study instead of the previously included caregiver. Patients can also participate if they don't have a caregiver. The caregivers of the additional patients will also be invited.

